## 6 Endpoints

The following endpoints are pre-defined for this study.

## 6.1 Primary Endpoint: Sum of Parts 1, 3, and 4 of UDysRS

The primary endpoint is the mean change and % change from Baseline (Visit 2) to Week 3/5 (Visit 3) and Week 8/10 (Visit 5) in the sum of Parts 1, 3, and 4 of the Unified Dyskinesia Rating Scale (UDysRS) while the patient is in the peak “ON” state and experiencing maximal peak dose dyskinesia.

The sum of Parts 1, 3, and 4 of the UDysRS will be calculated as the sum of Part 1 (historical disability of ON-dyskinesia impact), Part 3 (objective impairment) and Part 4 (objective disability). The sum scores will be calculated as follows:

- Part 1: sum of UDysRS items 1-11; 0-44 points
- Part 3: sum of UDysRS items 16-22; 0-28 points
- Part 4: sum of UDysRS items 23-26; 0-16 points.

For the sum scores of Parts 1, 3 and 4, the following imputation rules will be used in case of incomplete data:

- Part 1: Part 1 is sum of Part 1A (item 1) and Part 1B (items 2-11)
  - If Part 1A (item 1) is missing, the Part 1 sum score will be set as missing.
  - If there is one missing item in Part 1B (items 2-11), the missing item will be replaced by the average of the non-missing items 2-11 from the same subject.
  - If there is more than one missing item in Part 1B (items 2-11), the Part 1 sum score will be set as missing.
- Part 3:
  - If there is one missing item in Part 3 (items 16-22), the missing item will be replaced by the average of the non-missing items 16-22 from the same subject.
  - If there is more than one missing item in Part 3 (items 16-22), the Part 3 sum score will be set as missing.
- Part 4:
  - If there is one missing item in Part 4 (items 23-26), the missing item will be replaced by the average of the non-missing items 23-26 from the same subject.
  - If there is more than one missing item in Part 4 (items 23-26), the Part 4 sum score will be set as missing.
- Sum of Parts 1, 3 and 4:
  - The sum of Parts 1, 3 and 4 will be calculated only if sum of Part 1, sum of Part 3 and sum of Part 4 are all non-missing, after applying the imputation rules presented above. Otherwise, the sum of Parts 1, 3 and 4 will be set as missing.

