### 9.4 Multiple Comparison/Multiplicity

Since the study was terminated early and the sample size is small no adjustment for multiplicity will be performed. Statistical testing and p-values will be evaluated based on totality of information in assessing efficacy and provided primarily for descriptive purposes.

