## 14 Analysis of Efficacy

Each primary and secondary endpoint of this study includes the comparison of each of the two dosages of pridopidine vs placebo and the two pooled active doses vs placebo.

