### 14.1 Primary Endpoint

The primary endpoint of this study is the mean change from Baseline (Visit 2) to Visit 3 and Visit 5 in the sum of Parts 1, 3, and 4 of the UDysRS. The difference in the primary endpoint between the groups (pridopidine 150 mg BID versus placebo, pridopidine 100 mg BID versus placebo) will be estimated using a MMRM using the EE1 and EE2 populations after imputing missing data under assumption of MAR. The model will include the observed changes from Baseline using Visits 3, 4, 5, 6 and 7 as the response values. The treatment difference at each visit will be estimated using contrasts. The MMRM will include the treatment group (pridopidine 150 mg BID, pridopidine 100 mg BID or placebo), visit (3, 4, 5, 6 or 7) and the interaction between the treatment group and visit as fixed factors. The baseline value will be used as a covariate in the model.

A separate analysis will compare pooled active vs placebo under same assumptions as above.

An unstructured covariance structure will be applied for MMRM. In case the model will not converge with the unstructured covariance structure, heterogeneous Toeplitz structure (TOEPH), Autoregressive with heterogeneity (ARH (1)), Heterogeneous variances with Compound Symmetry (CSH), Toeplitz (TOEP), Autoregressive(1) (AR(1)) or Compound Symmetry without heterogeneous variances (CS) covariance structure will be used instead in this order. The denominator degrees of freedom will be computed using the Kenward-Roger method.

The least square (LS) means, standard errors and LS mean differences between pridopidine 150 mg BID versus placebo and pridopidine 100 mg BID versus placebo at each visit along with the 95% confidence intervals (CIs) will be provided. The nominal p-values for the hypothesis testing will also be provided. Treatment difference will be assessed with a 2-sided alpha level of 0.05.

The EE1 and EE2 populations will be used for the primary efficacy analysis.

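### The SAP leaves 12 to 24 nominal primary comparisons unranked, so the lead proof-of-concept result can be chosen after unblinding

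*SAP*

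**What the plan says.** - **Scale and visit.** SAP 6.1: "The primary endpoint is the mean change and % change from Baseline (Visit 2) to Week 3/5 (Visit 3) and Week 8/10 (Visit 5"), for the sum of UDysRS Parts 1, 3 and 4. SAP 14.1 restates this for absolute change only: "The primary endpoint of this study is the mean change from Baseline (Visit 2) to Visit 3 and Visit 5". It specifies a mixed model for that change and none for percent change.
- **Contrast.** SAP 14 calls for "comparison of each of the two dosages of pridopidine vs placebo and the two pooled active doses vs placebo". In 14.1 the pooled contrast has its own model: "A separate analysis will compare pooled active vs placebo under same assumptions as above".
- **Population.** SAP 14.1: "The EE1 and EE2 populations will be used for the primary efficacy analysis". SAP 5.1 ties EE1 to being on treatment at Visit 3 and EE2 to being on treatment at Visit 5. Neither is ranked first.
- **Level.** SAP 14.1: "Treatment difference will be assessed with a 2-sided alpha level of 0.05", and also "The nominal p-values for the hypothesis testing will also be provided".
- **Multiplicity.** SAP 9.4 says that "no adjustment for multiplicity will be performed", because of early termination and small size. It says p-values will be weighed with all the evidence on efficacy and serve mainly as description.
- **Priority.** SAP 3.1 sets the primary objective at Visit 5, for the doses separately and combined, and then adds 100 mg BID versus placebo at Visit 3. SAP 3 links the pooled doses with Visit 5. Neither names a lead comparison.

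SAP 2 and 17 state that the SAP supersedes the protocol, so the protocol's ordered testing does not supply a lead result either.

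**The concern.** SAP 4 recasts the terminated trial as proof of concept, so someone will read a yes-or-no signal from it. Scale, visit, contrast and population are all open within the primary endpoint. Several highly correlated results will therefore have an equal right to be called primary once the data are seen. Weighing the totality of evidence gives no rule for which result leads when they disagree, for example when pooled change at Visit 5 is unremarkable but percent change for one dose at Visit 3 reaches p<0.05.

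What is at stake is how the result is read and reported. With fewer than 30 patients (SAP 9.3), a result picked from a dozen or more is a weak basis for a decision on further development. A result named in advance can be taken at face value, with its confidence interval.

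**Working it through.** **1. The plan's own figures.** The documents give no error rate for the set of primary comparisons. The one design calculation, in SAP 7, is for a single two-sample t-test: 8.5 points, SD 13, two-sided 0.05, 38 per arm for 80% power. It reproduces: the exact noncentral t gives 79.2% at 37 per arm and 80.3% at 38. It assumed 38 per arm, whereas the trial stopped with fewer than 30 in total.

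**2. Counting the comparisons.**
- Modelled in 14.1 (change only): 2 visits × 3 contrasts × 2 populations = 12.
- If percent change from 6.1 is also tested: 12 × 2 = 24. This is an upper bound, because no percent-change model is specified.
- Visits 4, 6 and 7 are also estimated but are not counted, since 6.1 does not make them primary.

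**3. Independence as a ceiling.** 1 − 0.95^12 = 46.0% and 1 − 0.95^24 = 70.8%. These do not apply, because the tests are strongly correlated. For 1:1:1 allocation the two dose contrasts correlate 0.5, since they share the placebo arm. Each dose contrast correlates 1.5/√(2 × 1.5) = 0.866 with the pooled contrast. The three contrasts alone, at one visit, give about 9.7%.

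**4. Simulation under no effect.** All of these inputs are assumptions except the SD of 13, which is borrowed from SAP 7: 7 to 9 per arm; baseline mean 40, SD 12; SD of change 13; visit correlation 0.5 to 0.7; EE2 a random 80% of EE1; baseline-adjusted ANCOVA in place of the planned MMRM with imputation.

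| Set of tests | Any p<0.05, either direction | Any p<0.05 favouring pridopidine |
|---|---|---|
| One named test | 5% | 2.5% |
| 12 (change only) | about 21-23% | about 10-12% |
| 24 (adding percent change) | about 26-28% | about 12-14% |

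A further run of 6,000 trials per setting gave 21-25% and 25-30% in either direction, and 10.5-12.5% and 12.6-14.9% in the favourable direction. The table is therefore good to about two percentage points.

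**5. Wider correlations.** The 24 tests were also treated as multivariate normal, with correlations of 0.3-0.8 between visits, 0.8-0.95 between scales and 0.7-0.95 between populations. The result is 22.9-40.3% in either direction and 11.5-20.9% in favour of pridopidine.

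**6. A narrower reading.** Follow SAP 3.1 closely: at Visit 3, both active arms together versus placebo in EE1, because both are then on 100 mg BID; at Visit 5, three contrasts in EE2; change only. That is 4 tests, giving about 13-14% in either direction and about 7% favourable.

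**The case against.** The strongest reply is that the SAP does not claim what a multiplicity criticism presupposes. Section 9.4 discloses that nothing is adjusted and why, 14.1 labels the p-values nominal, and no rule turns one p<0.05 into a successful trial. For a terminated study of this size that is defensible, and it stands. A reader might infer that a promised 5% familywise rate is being broken without saying so. The documents do not support that, because no such rate is promised.

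The second reply is that SAP 3.1 already gives some order: Visit 5 comes first and Visit 3 is an addition. EE1 and EE2 are also each defined around one visit, so crossing both populations with both visits may overcount. This stands in part. It narrows the field, to 4 tests on the reading in step 6. But 6.1 and 14.1 put the two visits on an equal footing and use both populations without saying which goes with which. Even Section 3.1 keeps three contrasts at Visit 5.

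Neither reply deals with the remaining gap. Declining to adjust p-values and declining to say which estimate leads are separate choices, and small size justifies only the first.

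**Conclusion.** The point holds as one about designation. The SAP's primary endpoint comprises 12 unranked nominal tests, or up to 24 with percent change, and the lead result can be settled after unblinding. It should be corrected, but it does not invalidate the analysis.

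Under the assumptions in step 4, the chance of at least one nominally significant result with no true effect is about 21-23% for 12 tests and 26-28% for 24 (23-40% over the wider correlations). In favour of pridopidine it is about 10-12% and 12-14% (up to about 21%), against 2.5% for one test. Arm sizes, correlations and EE1/EE2 overlap are not in the documents, so these figures show a scale and are not properties of the plan.

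A reader might infer that roughly one null trial in four would be declared positive for pridopidine. That goes too far. The one-in-four figure counts results in either direction, including those where pridopidine looks worse. Its upper version includes percent-change tests that 14.1 does not specify. The SAP also contains no rule for declaring the trial positive.

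**What to change.** Before unblinding, name one lead comparison in SAP 6.1 and repeat it in 14.1: absolute change from baseline in the sum of UDysRS Parts 1, 3 and 4 at Visit 5, pooled active versus placebo, in one named population. This is consistent with SAP 3 and 3.1, which point to Visit 5 and link the pooled doses with it, though those sections do not dictate the choice. Designate percent change, Visit 3, the single-dose contrasts and the other population as supportive, each with its estimate and 95% confidence interval. The descriptive stance of 9.4 can stay, and no p-value adjustment is needed.

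The cost is SAP wording only. SAP 2 says the plan is being finalised before database lock and unblinding, so there is time. No data or analyses are lost. The one downside is that the supportive results can no longer be called primary.

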## 6.2 Secondary Endpoints

Secondary endpoints are defined as below:

### 6.2.1 ON time without troublesome dyskinesia and other endpoints based on “ON/OFF” home diary

Mean actual value and mean change from Baseline (Visit 2) to all post-baseline visits in ON time without troublesome dyskinesia based on “ON/OFF” home diary completed by the subjects during 3 consecutive 24 hour intervals will be evaluated as a secondary endpoint. The daily ON time without troublesome dyskinesia is defined as the sum of daily ON time without dyskinesia and daily ON time with non-troublesome dyskinesia.

This endpoint will be presented both as daily ON time without troublesome dyskinesia during waking hours and as total number of hours with ON time without troublesome dyskinesia, normalized to a 16-hour waking day.

The Baseline is defined as the home diary obtained on 3 consecutive days prior to the Baseline visit (Visit 2). The diaries collected during the Maintenance Period, on 3 consecutive days prior to Visit 4 (Week 5/7), Visit 5 (Week 8/10), Visit 6 (Week 11/13) and Visit 7 (Week 14/16) will be used as response variables. In case of missing or non-valid diary days during the 3 consecutive days prior to the visits during the Maintenance Period, the last 3 recorded days between Visits 3-4 (for Visit 4), 4-5 (for Visit 5), 5-6 (for Visit 6) and 6-7 (for Visit 7), but no more than 7 days before the visit with non-missing and valid diary data will be used instead. In case of missing or non-valid diary days before Baseline, the 3 last non-missing and valid diary days prior to the first dose of study drug will be used regardless of time between the day when the diary was completed and the Baseline visit.

The validity of the diary entries will be checked prior to including a diary day in the summary calculations. Only valid diary days will be included in the diary summarizations. The diary endpoints will be derived as defined below.

- A day will be considered as being valid if at least 44 of the 48 half hour periods during the day have been completed per instructions. That is, for each half hour period, only one entry among the responses (Asleep, OFF, ON without dyskinesia, ON with non-troublesome dyskinesia, or ON with troublesome dyskinesia) has been checked. The entry will not be used if no responses are checked or more than one response is checked. If there are duplicate entries (i.e., multiple entries recorded with same date and time interval), the worst entry will be used for the date and time interval in question. The worst entry will be defined in the following order: OFF, ON with troublesome dyskinesia, ON with non-troublesome dyskinesia, ON without dyskinesia, Asleep. On without troublesome dyskinesia
- The diary data expressed as hours will be normalized to 16 waking hours per day. The daily ON time without troublesome dyskinesia will be extrapolated to a 16-hour period by determining the percentage of ON time without troublesome dyskinesia among accurately recorded entries, excluding Asleep time and missing/non-valid recordings, and by multiplying this percentage by 16 hours.
- The mean daily ON time without troublesome dyskinesia prior to each visit will be calculated as mean value of the valid days documented in the subject’s diary prior to that visit. In case there are gaps within the 3 days preceding the visit, the last 3 recorded days before the visit will be used regardless of the gaps (as defined above). If there are more than 3 valid days, only the last 3 days will be used. If

there are only 2 valid days, the average of these days will be used. In case there is only 1 valid day, the visit will be considered missing.

As above the following will also be summarized:

- ON time without any dyskinesia
- OFF time

### **6.2.2 The above analysis will be generated for the EE1 and EE2 populations. Total UDysRS score - Sum of Parts 1 to 4**

Mean change and % change from Baseline (Visit 2) to Week 3/5 (Visit 3) and Week 8/10 (Visit 5) in the total UDysRS score (Parts 1 to 4) will be evaluated as a secondary endpoint. The total UDysRS score will be calculated as the sum of Part 1 (historical disability of ON-dyskinesia impact), Part 2 (historical disability of OFF-dyskinesia impact), Part 3 (objective impairment) and Part 4 (objective disability).

The sum scores for Parts 1, 3 and 4 will be calculated similarly as for the primary endpoint. The sum score of Part 2 will be calculated as follows:

- Part 2: sum of UDysRS items 12-15; 0-16 points

For the sum scores of Parts 1, 2, 3 and 4, the following imputation rules will be used in case of incomplete data:

- Part 1: see definition of the primary endpoint
- Part 2: Part 2 is sum of Part 2A (item 12) and Part 2B (items 13-15)
  - If Part 2A (item 12) is missing, the Part 2 sum score will be set as missing.
  - If there is one missing item in Part 2B (items 13-15), the missing item will be replaced by the average of the non-missing items 13-15.
  - If there is more than one missing item in Part 2B (items 13-15), the Part 2 sum score will be set as missing.
- Part 3: see definition of the primary endpoint
- Part 4: see definition of the primary endpoint
- The total UDysRS score
  - The total UDysRS score, i.e. the sum of Parts 1, 2, 3 and 4 will be calculated only if sum of Part 1, sum of Part 2, sum of Part 3 and sum of Part 4 are all non-missing, after applying the imputation rules presented above. Otherwise, the total UDysRS score will be set as missing.

The above analyses will be presented for the EE1 and EE2 populations.

### **6.2.3 Unified Parkinson's Disease Rating Scale (UPDRS) Part 2**

Mean change and % change from Baseline (Visit 2) to each post baseline assessment in the score of Unified Parkinson's Disease Rating Scale (UPDRS) Part 2 will be evaluated as a secondary endpoint. The

## Statistical Analysis Plan

UPDRS Part 2 sum score will be calculated as the sum of UPDRS items 5-17 (range 0-52 points). The Part 2 sum score will only be calculated if all 13 items have been completed. In case of at least 1 missing item, the whole score will be set as missing.

The above will be summarized for the EE1 and EE2 population.

### 6.2.4 Proportion of Responders

Proportion of responders (with improvement in dyskinesia and improvement in dyskinesia with no worsening in parkinsonian motor function separately) at Visits 3 and 5 will be evaluated as a secondary endpoint. The improvement in dyskinesia is defined as  $\geq 30\%$  improvement in UDysRS score (Parts 1, 3, and 4) from Baseline (Visit 2) and no worsening from Baseline (Visit 2) in motor function is defined as  $\leq 30$  minutes increase in OFF time from Baseline (Visit 2).

In addition, proportion of responders with improvements of  $\geq 35\%$ ,  $\geq 25\%$  and  $\geq 20\%$  will also be summarized.

A Fisher's exact test will be used to compare differences between each of the active treatment group vs placebo.

The UDysRS score (Parts 1, 3, and 4) will be derived as defined in Section 6.1 and the OFF time as defined in Section 6.2.8, represented as hours normalized to a 16-hour waking day. The percentual change in the UDysRS score from baseline will be calculated as the absolute change divided by the baseline value. A decrease in the UDysRS score indicates improvement.

The visits with missing data in either the UDysRS score (Parts 1, 3, and 4) or in OFF time will be set as missing. However, a sensitivity analysis will be conducted by considering missing data as non-improvements.

The above will be summarized for the EE1 and EE2 population.

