3.1 Study Design

This is a Phase 2B, multicenter, randomized, three-arm, parallel-group, double-blind, placebo-controlled study to evaluate the efficacy, safety, and PK of pridopidine 100 mg BID and 150 mg BID vs placebo for the treatment of PD-LID, experiencing dyskinesia.

Following a minimum of a 3-week and up to 9-week screening period, patients will be randomized in a 1:1:1 ratio into one of the three treatment arms: pridopidine 100 mg BID, pridopidine 150 mg BID or exactly matching placebo. Patients randomly assigned to the active treatment arms will undergo a dosage regimen titration period during which they will be treated with pridopidine 75 mg once every other day (Q48h) for 1 week, followed by pridopidine 75 mg once daily (QD) for 1 week, pridopidine 75 mg BID for 1 week, and finally by 100 mg BID for the fourth and final week of titrations. Maintenance treatment with pridopidine 100 mg BID or 150 mg BID will then continue for an additional 12 weeks. Patients randomly assigned to the placebo arm will receive a matched placebo for the duration of the 16-week active treatment period. Upon completion of the 16-week active treatment period, patients will undergo a 4-day down titration phase, which will be followed by a safety follow-up visit at Visit 8 (2 weeks after completion of the 16-week active treatment period).

During the 4-week titration period, for patients who suffer from symptoms indicating worsening of PD, the levodopa regimen may be adjusted until the regimen is optimal according to the Investigator's judgment. This optimal regimen must be obtained within the 4 weeks titration period and cannot be lower than the total daily levodopa dose regimen at the time of screening.

The study duration (from first patient randomized to last patient last visit) will be approximately 12 months.

The study design is presented in [Figure 1](#).

Figure 1 Study Design

Study week	3-9 weeks				Maintenance												Down titration																				
	Screening				Maintenance								Down titration																								
Visit (V) #	Screening				Maintenance								Down titration																								
	V1	V1.1*			V3	V4			V5	V6			V7 EoT	V8 SFU																							
Study day	(-21) or (-63) -0	(-21)-0			1	8	15	22	29	43	70	91	112	126																							
Visit measures	All Screening Procedures	UDysRS part 4				Safety				Safety				Safety																							

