### 3.2 Secondary Objectives

1. To determine if the effect of pridopidine (100 mg BID, 150 mg BID and pooled 100+150 mg BID) vs placebo is associated with changes (worsening or improvement) in parkinsonian features at Weeks 3/5 and 8/10 (Visits 3 and 5).
2. To evaluate the effect of pridopidine (100 mg BID, 150 mg BID and pooled 100+150 mg BID) vs placebo on measures of global improvement, activities of daily living, and quality of life in subjects with PD LID at Weeks 3/5 and 8/10 (Visits 3 and 5).

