### 6.2.5 UPDRS Part 3 as Measured Immediately Prior to the In-clinic L-DOPA Dose

Mean change and % change Baseline (Visit 2) to each post baseline visit in the UPDRS Part 3 as measured immediately prior to the in-clinic L-DOPA dose will be evaluated as a secondary endpoint. The UPDRS Part 3 sum score will be calculated as the sum of UPDRS items 18-31 (range 0-108 points). The Part 3 sum score will only be calculated if all 27 items have been completed. In case of at least 1 missing item, the whole score will be set as missing.

The above will be summarized for the EE1 and EE2 population.

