## 10 Subjects Disposition, Demographic and Other Baseline Characteristics

The following will be summarized in the Subject Disposition table.

- A summary of the number of subjects in each of the analysis populations.
- The number and percentage of subjects who were randomized but not treated.
- The count and percentage of subjects who completed or discontinued from the study or treatment. For those who discontinued from the study or treatment, the primary reason for discontinuation from the study or treatment will be presented.

Demographics and baseline characteristics will be summarized descriptively for the Safety Population, by treatment group and overall. For categorical endpoints, categories for missing data will be presented.

The following variables will be summarized:

- Demographics: age (continuous, calculated as date of informed consent minus date of birth, divided by 365.25), age categorized as <65 years versus  $\geq 65$  years, gender, ethnicity, race, height, weight, BMI (calculated as weight [kg] divided by squared height [ $m^2$ ]) and country. In case of missing day of birth, the day will be imputed as 15. In case of missing month of birth, the month will be imputed as 6.
- PD history: time since diagnosis of PD, time since start of levodopa treatment and time since onset of levodopa-induced dyskinesia, all measured in years at time of informed consent
- Report of direct observation of ON-time with dyskinesia during half-hour periods of the screening visit
- Baseline dyskinesia status: total score on UDysRS part 4 disability scale.
- Cognitive status: Mini-Mental State Examination (MMSE) total score (as categorical, % of subjects with a score of 30, 29, 28, 27, 26 or <26)
- Distribution of Modified Hoehn and Yahr stages
- Total daily levodopa dose (mg) and distribution of dosing frequency at Screening.

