## 11 Prior and Concomitant Medications

Prior and Concomitant medications data are coded using WHODD Global-B3-Sep 2018 and will be presented in listings with no summary tables.

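### The SAP 6.2.4 composite responder can count PD worsening that was corrected with levodopa as no worsening, and no summary table compares levodopa change by arm

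*SAP*

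**What the plan says.** **Levodopa rule.** Protocol 3.1 provides that in the 4-week titration, "for patients who suffer from symptoms indicating worsening of PD, the levodopa regimen may be adjusted until the regimen is optimal" in the investigator's judgement. The adjusted regimen must be reached within titration and "cannot be lower than the total daily levodopa dose regimen at the time of screening". Protocol 3.1.2, 5.10 and Table 4 footnote j repeat the rule. Protocol 3.1.1 and inclusion criterion 10 then hold anti-PD treatment stable through maintenance.

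**Objective.** Secondary objective 1 (SAP 3.2) asks whether the effect of pridopidine against placebo "is associated with changes (worsening or improvement) in parkinsonian features at Weeks 3/5 and 8/10 (Visits 3 and 5").

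**Endpoints.** SAP 6.2.4 evaluates responders "with improvement in dyskinesia and improvement in dyskinesia with no worsening in parkinsonian motor function separately". There, "no worsening from Baseline (Visit 2) in motor function is defined as" a rise in OFF time of at most 30 minutes. Levodopa has no part in the definition. UPDRS Part 2 and OFF time are also analysed in their own right, and change "in the UPDRS Part 3 as measured immediately prior to the in-clinic L-DOPA dose will be evaluated as a secondary endpoint" (SAP 6.2.5). All three use repeated-measures models adjusted only for their own baseline (SAP 9.1, 14.2.1).

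**Levodopa outputs.** The baseline characteristics in SAP 10 include "Total daily levodopa dose (mg) and distribution of dosing frequency at Screening". Under SAP 11, prior and concomitant medications "will be presented in listings with no summary tables".

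**The concern.** Secondary objective 1 exists to show whether any antidyskinetic effect is bought at the price of parkinsonian worsening. Under the protocol's own rule, the trigger for adjusting levodopa is worsening of PD. If a dose of pridopidine worsened PD, one expected sign would be more levodopa increases in that arm. If the increases worked, OFF time and UPDRS would look unchanged.

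The plan tabulates the measures that the increase would correct. It does not tabulate the increase itself. A reader of the summary tables could not tell an arm with no worsening from an arm whose worsening was treated.

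**Working it through.** No figure in the plan bears directly on this point. The check sets the timing, the definition and the outputs side by side.

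**1. Timing under protocol v2.0 (Protocol 5.2 and Table 4; SAP 6.2.1)**

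| Event | Study day | UPDRS | Diary (OFF time) |
|---|---|---|---|
| Baseline, Visit 2 | 1 | yes | yes (screening diaries) |
| Levodopa adjustment window | 1–28 | none | none |
| Visit 3 | 29 ± 1 | none | none |
| Visit 4 | 43 ± 1 | yes | yes (3 days before) |
| Visit 5 | 70 ± 1 | yes | yes (3 days before) |

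The first scheduled post-baseline UPDRS falls 43 − 28 = 15 days after the window closes. The first diary days are nominally Days 40–42, so they start 40 − 28 = 12 days after it closes. No scheduled motor endpoint is read between the start of treatment and the end of the window. Because the regimen is then held stable, a correction made in titration is still in force at Visit 5.

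**2. Direction.** The adjusted regimen may not fall below the screening regimen. Relative to screening, total daily dose can only hold or rise.

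**3. Two hypothetical subjects.** Both improve by at least 30% on UDysRS Parts 1, 3 and 4, and both have an OFF-time rise of at most 30 minutes at Visit 5. Subject A had no PD worsening and no levodopa change. Subject B had PD worsening in titration, and levodopa was raised until OFF time recovered.

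| Planned output | Separates A from B? |
|---|---|
| Composite responder, SAP 6.2.4 | No: both are responders |
| OFF time, continuous | Not if OFF time has recovered |
| UPDRS Part 2 | Not if the adjustment restored it |
| UPDRS Part 3, before the in-clinic dose | Perhaps in part: pre-dose timing may lessen the masking |
| Levodopa dose table, SAP 10 | No: Screening only |
| AE tables, SAP 15.3 | Only if the worsening was judged unexpected (Protocol 6.5.1.9) |
| Concomitant medication listing, SAP 11 | Yes, by reading subject lines; no by-arm summary |

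**4. How coarse the responder rate is.** SAP 9.3 says the study stopped before 30 subjects were enrolled, so there were at most 29. With 1:1:1 allocation, 29 / 3 = 9.7, or about 10 per arm at most if the split was even. One subject is then 1 / 10 = 10 percentage points of an arm's rate, and more if the efficacy evaluable sets are smaller. In the pooled active group, of about 19, one subject is 1 / 19 = 5 points. This is the weight of one reclassified subject. It does not estimate how many would be reclassified.

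**The case against.** The case for leaving the plan alone has real force.

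- **The information is there.** SAP 9 puts all data into listings, generally sorted by study drug. With fewer than 30 subjects, a reader can count levodopa changes by arm. This stands: what is missing is a summary, not the data. But a count made from listings after unblinding is post hoc. SAP 2 says the plan is being finalised before lock and unblinding, which is the time to specify it.
- **Objective 1 does not rest on one composite.** UPDRS Parts 2 and 3 and continuous OFF time also inform it. This stands too, though all are read on the adjusted regimen with no levodopa term.
- **The definition is a legitimate choice.** Motor function on an investigator-optimised regimen, under the same blinded rule in every arm, is a coherent treatment-policy reading. I accept this, so the main responder definition need not be replaced.
- **The study is descriptive.** It is now a small proof-of-concept study with p-values given mainly for description (SAP 4, 9.4). That limits the stakes. However, SAP 9.4 judges efficacy on the totality of information, and levodopa change by arm belongs in it.

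**Conclusion.** The point holds as a gap in reporting and sensitivity analysis. As written, the composite counts treated worsening as no worsening, and no summary table lets a reader of secondary objective 1 see how much treatment was needed. The size is unknown because the documents give no adjustment rate. The conclusion rests on the levodopa rule in protocol v2.0. The SAP also covers subjects on the v1.1 two-week titration, whose protocol text is not available, so the rule cannot be confirmed for them.

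A reader might infer three stronger things that the documents do not support:

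- **That masking occurred, or differed by arm.** The text shows only that it is possible.
- **That the UDysRS difference is diluted by extra levodopa.** Protocol 1.1.1 calls levodopa dosage a risk factor for developing dyskinesia. It says nothing about the effect of a dose change on UDysRS over weeks in established dyskinesia, so no number of points can be attached.
- **That the motor outputs are uninformative.** Pre-dose UPDRS Part 3 and AE reports of unexpected worsening may catch part of it.

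**What to change.** 1. **SAP 10/11.** Add a by-arm table (100 mg BID, 150 mg BID, pooled, placebo) with the number of subjects having any increase in total daily levodopa dose from Baseline, and the mean change in dose, at Visits 3 and 5. Read the Visit 5 figures beside the UPDRS and OFF-time results. At Visit 3 the table stands alone, because neither UPDRS nor diaries are collected then.
2. **SAP 6.2.4.** Add a pre-specified sensitivity analysis of the Visit 5 composite in which a subject whose total daily levodopa dose exceeds the baseline dose does not meet the motor component. Keep the main definition. The section already carries one sensitivity analysis, for missing data, so the form is familiar.

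Name the data source for dose. Protocol 3.1.4 and 5.9 record levodopa doses around diary and clinic days, and 5.10 sends medication changes to the eCRF. However, the minimum stated in 5.10 is drug name and dates, so availability of dose at Visit 3 should be confirmed.

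I would not add a re-run that sets values after a levodopa increase to missing. Under v2.0 an adjusted subject would lose every scheduled post-baseline efficacy value. The missing-at-random assumption would be doubtful because worsening triggers the increase, and the run could itself hide worsening.

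The cost is SAP wording and one or two outputs. No clinical rule changes. The sensitivity responder rate may be slightly less favourable than the main one.
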